### 9.1.1. Footnotes for the Schedule of Events (Original Protocol)

1. The screening visit may occur up to 14 days prior to the baseline visit (day 1). For participants at sites with rapid RT-PCR testing, screening and baseline visits may occur on the same day.

Participants who are unable to complete screening requirements within the screening period are allowed to be rescreened once, after consultation with the Sponsor.

2. During all EAP and follow-up visits, the site will remind participants to call the site as soon as possible if they experience any changes in their health, including any symptoms possibly related to COVID-19, and ensure that participants have the correct contact information to notify the site.

On visit days when sample collection or dosing is not required, the information indicated in the schedule may be collected remotely without an in-person visit.

For participants who do not require blood samples collected for drug concentration (PK), the day 8 visit may be performed remotely.

3. Participants will be offered post-infection treatment with casirivimab+imdevimab if the criteria provided in Section 6.4.4 are met. The post-infection treatment to be offered is also defined in Section 6.4.4. The confirmatory visit and post-infection treatment visit may occur on the same day. The confirmatory visit may also occur on the same day as a scheduled study visit. If visits occur on the same day, assessments for both visits must be collected (but not duplicated).

4. Collection for screening test must fulfill the window specified in the eligibility criteria (Section 7.2.1). If collection is performed outside of this window, testing must be repeated prior to randomization. Refer Section 9.2.1.4 for requirements related to screening test and baseline tests for SARS-CoV-2 infection. Participants who were negative according local testing but positive by central testing will discontinue study drug and enter the follow-up period. Refer to Section 6.4.7 for more information.

5. Dosing will be administered after all assessments and sample collections are completed.

6. Vital signs (defined in Section 9.2.5.1) will be collected before study drug administration. On day 1, participants will be observed for at least 15 minutes after completion of study drug administration.

7. Refer to Section 10.1 for AE monitoring and reporting guidelines.

8. The indicated blood samples may be collected at either day -1 or day 1 but must be collected prior to drug administration.

Samples for serological assays will be used for retrospective analysis (Section 9.2.8.1) and the results will not be reported to study sites.

9. During any early termination visit, COVID-19 signs and symptoms will be assessed only for participants who were RT-PCR positive and entered follow-up without completing all study visits during the EAP.

10. Samples for drug concentration (PK) and immunogenicity (ADA) will only be collected in the first 600 participants who are enrolled at participating sites.
11. Actual dosing time and drug concentration sample (PK) collection times will be recorded. For PK sample collection on dosing days, samples must be collected prior to dosing.
12. The window for pre-dose immunogenicity (ADA) sample collection should be as close to administration of study drug as is reasonable. Actual dosing time and ADA sample collection times will be recorded.
13. The assessments and procedures in this section only apply to participants with suspected COVID-19, confirmed COVID-19 symptoms, or laboratory confirmed SARS-CoV-2 infection, as indicated. Note the following:
  - The collections and assessments indicated in this section will be performed **in addition** to collections and assessments indicated in the scheduled visits.
  - Refer to Section [6.4](#) for monitoring, evaluation, and additional procedures for participants with suspected COVID-19 or laboratory-confirmed SARS-CoV-2 infection.
  - Comprehensive vital sign assessment includes standard vital sign assessment (defined in Section [9.2.5.1](#)), SpO2, and respiratory rate.
  - NP swabs for central lab RT-qPCR testing are collected once every 7 days ( $\pm 1$  day) until 2 consecutive tests are negative.
  - Clinician assessment of COVID-19 signs and symptoms is performed every 7 days ( $\pm 1$  day) until 2 consecutive RT-qPCR tests are negative. Signs and symptoms will continue to be evaluated during the scheduled visits of the follow-up period.

#### **9.1.2. Footnotes for the Schedule of Events (Protocol Amendment 2)**

1. Approximately 85 days after the final dose of study drug (ie, the optional final dose of casirivimab+imdevimab defined in protocol amendment 2, or the final assigned casirivimab+imdevimab or placebo dose for participants who do not receive the optional dose).
2. Informed consent may be obtained at the dosing visit, or at any time prior to the visit via remote consent (if available and allowable at the study site).
3. Applicable to participants who consent to receive a final optional dose of 1200 mg SC casirivimab+imdevimab. The optional dose may be administered to all participants regardless of treatment assignment at randomization. However, participants will not be eligible to receive this dose if they have already received casirivimab+imdevimab as post-infection treatment. The dose will be recorded.
4. Vital signs (defined in Section [9.2.5.1](#)) will be collected before study drug administration and at least 60 minutes after completion of study drug administration.
5. Refer to Section [10.1](#) for AE monitoring and reporting guidelines.

6. Note that all assessments and procedures related to participants with suspected COVID-19 are optional for both the study site and the study participant. Refer to [Protocol Amendment 2 Procedures](#) for additional information.
7. Clinician assessment of sign or symptoms may occur remotely. If remote assessment is performed, a confirmatory site visit for laboratory testing of SARS-CoV-2 can optionally occur after a clinician deems that the signs or symptoms are related to COVID-19.
8. Comprehensive vital sign assessment includes standard vital sign assessment (defined in Section [9.2.5.1](#)), SpO2, and respiratory rate.
9. Note that samples for local and central laboratory testing of SARS-CoV-2 may be collected on the same day; the results of local testing are not required prior to sample collection for central testing.

### **9.1.3. Early Termination Visit**

Participants who withdraw from the study will be asked to have an early termination (ET) visit consisting of the assessments indicated in the Schedule of Events.

### **9.1.4. Unscheduled Visits**

All attempts should be made to keep participants on the study schedule. Unscheduled visits may be required for participants with suspected COVID-19; refer to Section [6.4](#) for additional information.

Unscheduled visits may also be necessary to repeat testing following abnormal laboratory results, for collection of NP swabs, blood, serum, or plasma, for follow-up of treatment-emergent SAEs, treatment-emergent AESIs, or for any other reason, as warranted.

## **9.2. Study Procedures**

This section describes the procedures and collections that will be performed in this study. Procedures and collections will occur according to the Schedule of Events.

### **9.2.1. Procedures Performed at Screening**

The following procedures will be performed for the purpose of determining study eligibility or characterizing the baseline population: informed consent, medical history, demographics (including age, sex, race), weight, height, screening assessment for SARS-CoV-2 infection.

#### **9.2.1.1. Informed Consent**

Informed consent (and assent, as applicable) must be obtained according to the requirements described in Section [13.2](#).

#### **9.2.1.2. Medical History**

Medical history will include, but not be limited to the following:

- Prior COVID-19 infection
- COVID-19 vaccination record

- Menopausal history
- Pregnancy or breastfeeding status, if applicable

### **9.2.1.3. Weight and Height**

Body weight will be assessed using calibrated scales. During weight assessment, participants should not wear shoes. Body weight will be recorded to the nearest 0.1 kg.

Height will also be recorded.

### **9.2.1.4. Screening and Baseline Assessments for SARS-CoV-2 Infection**

During the screening period, the investigator or designee will verify that the participant has tested negative for SARS-CoV-2 within the time period specified in Section [7.2.1](#). The screening assessment for SARS-CoV-2 infection will be performed locally using an approved or authorized diagnostic RT-PCR assay, performed according to the study site's standards and procedures.

For local screening test, a nasopharyngeal (NP) swab sample is the preferred sample type, but other samples (eg, nasal, oropharyngeal, saliva) are acceptable if they are collected according to local standards. For tests performed at screening, the local testing result, specimen type, assay type, and date of the test will be recorded in the eCRF.

Baseline SARS-CoV-2 RT-qPCR testing will be performed by a central laboratory NP swab test on day 1. The qualitative results of this baseline central SARS-CoV-2 RT-qPCR will be reported back to the corresponding study site but will not be required prior to study drug administration on day 1.

### **9.2.2. Randomization**

Refer to Section [8.5](#).

### **9.2.3. Study Drug Administration**

Refer to Section [8.1](#).

### **9.2.4. Efficacy Procedures**

#### **9.2.4.1. Post-Baseline Assessments for SARS-CoV-2 Infection**

Refer to Section [6.4](#) for additional information regarding post-baseline testing for SARS-CoV-2 infection.

#### **9.2.4.2. Clinician Assessment of COVID-19 Signs and Symptoms**

COVID-19 signs and symptoms will be evaluated by a study clinician (investigator or designee) during each study visit as indicated in the Schedule of Events. Participants with suspected COVID-19 will also undergo an evaluation of symptoms as soon as possible (within 48 hours of symptom onset, if feasible), and those with a positive SARS-CoV-2 RT-PCR will undergo weekly assessment of signs and symptoms (refer to Section [6.4](#) and the Schedule of Events for additional information).

**Clinical Evaluation.** The clinician (investigator or designee) will evaluate the participant for signs of COVID-19 and query participants and/or their parent(s) or guardian(s) for any symptoms of COVID-19.

Information regarding symptoms should be obtained in an unsolicited fashion, allowing the participant and/or participant's parent(s) or guardian(s) to spontaneously report events. Solicitation of specific symptoms should be avoided.

**Source Documentation.** For each symptom, the start (onset) date, end date, and severity will be recorded (mild, moderate, severe) in the participant's medical record (source document). It is important to record this information in the source document, to ensure that the temporal dimensions of each sign or symptom are captured.

**Event of Interest.** A sign or symptom recorded in the source document will subsequently be recorded as an event of interest (EI) if it meets all of the following conditions:

- The participant has laboratory-confirmed SARS-CoV-2 infection (refer to Section [6.4](#) for details)
- The sign or symptom falls within the broad term definition ([Table 3](#))
- The sign/symptom onset date and the date of collection for the positive sample occurring within  $\pm 7$  days of one another

For each EI, and during each visit for which signs and symptoms are evaluated, the following minimum information will be recorded:

- The sign or symptom, with start (onset) calendar date, end calendar date, and severity (mild, moderate, severe)
- Confirmatory local RT-PCR test result and date of sample collection
- Confirmatory central RT-qPCR test result and date of sample collection
- Weekly central RT-qPCR test results and dates of sample collection
- Record of any post-infection treatment with casirivimab+imdevimab administered

Note that any sign or symptom corresponding to a grade  $\geq 3$  TEAE will also be recorded and used for safety evaluation as described in Section [10.1](#).

**Table 3: Broad Term Definition of COVID-19 Signs and Symptoms**

• Body aches such as muscle pain or joint pain	• Chest pain	• Chills
• Confusion	• Cough	• Diarrhea
• Dizziness	• Fatigue	• Feverish
• Fever $\geq 38.0^{\circ}\text{C}$	• Headache	• Loss of appetite
• Loss of taste / smell	• Nausea	• Pressure / tight chest
• Rash	• Red or watery eyes	• Runny nose
• Shortness of breath / difficulty breathing	• Sneezing	• Sore throat
• Sputum / phlegm	• Stomachache	• Vomiting

### **9.2.4.3. COVID-19-Related Medically-Attended Visit Details, Immunocompromised Population Definition (Exploratory Outcome)**

A COVID-19-related medically-attended visit (MAV) will be defined as follows: hospitalization, ER visit, urgent care visit, physician's office visit, or telemedicine visit, with one of the reasons for the visit being COVID-19.

Medically-attended visits related to COVID-19, as determined by the investigator, will be recorded in the eCRF. Details will include at minimum:

- Type of visit (hospitalization, ER, urgent care, physician's office visit, telemedicine)
- Date of visit
- If hospitalized due to COVID-19, length of visit
- Reason (list all COVID-19-related clinical manifestation[s] that prompted the medically-attended visit)
- If hospitalized due to COVID-19, whether ICU care was given
- If hospitalized due to COVID-19, whether mechanical ventilation was required
- Treatments given for COVID-19 (including, but not limited to, supplemental oxygen, corticosteroids, remdesivir, baricitinib, etc)

## **9.2.5. Safety Procedures**

### **9.2.5.1. Vital Signs**

Standard vital signs will include body temperature, blood pressure, and heart rate. Comprehensive vital sign assessment will additionally include SpO2 and respiratory rate.

Vital signs will be measured after the participant has been resting quietly for at least approximately 5 minutes and may be obtained in seated or supine position.

Temperature may be measured using the following methods: axilla, oral, tympanic, or temporal. Body temperature should be measured using the same method each time. Temperature should be measured after at least 5 minutes of rest (supine or sitting).

SpO2 will be measured using a fingertip or similar non-invasive device following 5 minutes of rest (inactivity) while supine, semi-recumbent, or sitting and will only be measured in the presence of a good SpO2 wave form.

### **9.2.5.2. Adverse Event Monitoring**

Refer to Section [10.1](#).

### **9.2.5.3. Concomitant Medications and Procedures**

Concomitant medications and procedures will be recorded as defined in Section [8.9](#).

#### **9.2.5.4. Pregnancy Test for Women of Childbearing Potential**

Pregnancy testing will be performed in women of childbearing potential (WOCBP) only. Serum or urine pregnancy test are both acceptable.

Participants who become pregnant will remain in the study and will continue to follow the Schedule of Events as planned. Refer to Section [10.1.3](#) for more information regarding pregnancy reporting.

#### **9.2.5.5. Pregnancy Status**

Pregnancy status and date of pregnancy, as applicable, will be recorded. Refer to Section [10.1.3](#) for reporting requirements.

#### **9.2.5.6. Vital Status**

Vital status (whether the participant is dead or alive) will be recorded, as well as the date of death, when applicable.

#### **9.2.5.7. Safety Information in Newborns of Study Participants**

The incidence and outcome of any SARS-CoV-2 infection will be collected for newborn infants of participants who were treated in the study and were pregnant at randomization or became pregnant at any time in the study. Note that this information is in addition to outcome reporting of all pregnancies (Section [10.1.3](#)).

#### **9.2.6. Drug Concentration and Measurements**

Samples will be collected at the timepoints listed in the Schedule of Events. For information concerning unused samples and exploratory research, refer to Section [9.2.9](#).

#### **9.2.7. Immunogenicity Measurements and Samples**

Samples for immunogenicity assessment will be collected at the timepoints listed in the Schedule of Events. For information concerning unused samples and exploratory research, refer to Section [9.2.9](#).

#### **9.2.8. Pharmacodynamic/Biomarker Procedures**

##### **9.2.8.1. Serological Assays for Endogenous Anti-SARS-CoV-2 Antibodies**

Antibodies against the S protein RBD will be measured using the Elecsys® anti-SARS-CoV-2 S assay (anti-RBD total Ig, Roche) on samples collected at baseline. The results of this assay will be used to retrospectively analyze the data by the magnitude of baseline immune response to COVID-19 vaccines (see efficacy analysis set definitions in Section [11.3.1](#)). Neutralizing antibodies against SARS-CoV-2 will also be measured at baseline in all enrolled participants in order to determine if any measurable, endogenous humoral response was functional.

Additional anti-SARS-CoV-2 antibodies may also be measured on stored samples to further characterize participants' baseline serostatus. Any assays used post-baseline to measure antibody immunity will have been demonstrated not to be susceptible to interference from study drug.

#### **9.2.8.2. Serum and Plasma for Exploratory Research**

Serum and plasma collected and banked for exploratory research may be used for studies related to COVID-19 disease or vaccination, SARS-CoV-2, casirivimab, imdevimab, host and viral biological pathways, and other mechanisms related to safety, drug exposure, disease activity and clinical outcomes.

#### **9.2.8.3. Exploratory Virology and Viral Sequencing**

In support of public health initiatives to track SARS-CoV-2 genetic variants pre and post-treatment, viral genome sequencing will be performed on SARS-CoV-2 viral nucleic acid isolated from available nasopharyngeal (NP) swab samples collected during the study that have been confirmed positive by RT-qPCR for SARS-CoV-2 at the central laboratory.

The results of viral sequencing and related analyses may be reported outside of the study CSR in a separate report.

#### **9.2.9. Unused and Residual Biological Samples**

Any biological samples collected during the study which are not used for their planned purpose, or for which material remains after their planned analysis, may be kept for up 15 years after study completion (or for a shorter time period if required per regional laws and regulations) for use in exploratory research related to COVID-19 disease or vaccination, SARS-CoV-2, casirivimab+imdevimab, host and viral biological pathways, and other mechanisms related to safety, drug exposure, disease activity and clinical outcomes.

#### **9.2.10. Exploratory Immunology Sub-Study (Optional; Separate Protocol)**

Whole blood samples may be collected as part of an optional sub-study at a select site(s) to study patients' endogenous immune activity and responses to COVID-19 vaccination, SARS-CoV-2 infection and infection by other pathogens such as, but not limited to, influenza. The samples may be used to characterize the cells and plasma to study immune function in these patients pre- and post-treatment using flow cytometry, RNA sequencing, cytokine profiling, and other methods. This sub-study will be described in a separate protocol and results will not be included in the CSR.

## 10. SAFETY EVALUATION AND REPORTING

### 10.1. Recording and Reporting Adverse Events

This study will collect and record the following targeted TEAEs:

- Treatment-emergent grade  $\geq 3$  AEs
- Treatment-emergent AEs leading to study drug discontinuation
- Treatment-emergent SAEs
- Treatment-emergent grade  $\geq 2$  hypersensitivity reactions
- Treatment-emergent grade  $\geq 3$  injection-site reactions

*Note: throughout Section 10, the term “AE” refers to the targeted list above.*

#### 10.1.1. General Guidelines

The investigator must promptly record all clinical events occurring during the study data collection, from the start of the pretreatment period to the end of on-treatment period (see Section 11.4.5.1). Medical conditions that existed or were diagnosed prior to the signing of the informed consent will be recorded as part of medical history. Abnormal laboratory values and vital signs observed at the time of informed consent should also be recorded as medical history. Any subsequent worsening (ie, any clinically significant change in frequency and/or intensity) of a pre-existing condition that is temporally associated with the use of the study drug should also be recorded as an AE.

At each visit, the investigator will determine whether any AEs have occurred by evaluating the participant. Adverse events may be directly observed, reported spontaneously by the participant or parent, or by questioning the participant or parent at each study visit. Participants and parents should be questioned in a general way, without asking about the occurrence of any specific symptoms. The investigator must assess all AEs to determine seriousness, severity, and causality, in accordance with the definitions in Section 10.2. The investigator’s assessment must be clearly documented in the site’s source documentation with the investigator’s signature. The investigator should follow up on SAEs (and AESIs) until they have resolved or are considered clinically stable; AEs should be followed until they are resolved or last study visit, whichever comes first.

Always report the diagnosis as the AE or SAE term. When a diagnosis is unavailable, report the primary sign or symptom as the AE or SAE term with additional details included in the narrative until the diagnosis becomes available. If the signs and symptoms are distinct and do not suggest a common diagnosis, report them as individual entries of AE or SAE.

Laboratory results, vital signs, and other diagnostic results or findings should be appraised by the Investigator to determine their clinical significance. Isolated abnormal laboratory results, vital sign findings, or other diagnostic findings (ie, not part of a reported diagnosis) should be reported as AEs if they are symptomatic, lead to study drug discontinuation, dose reduction, require corrective treatment, or constitute an AE in the Investigator’s clinical judgment.

For events that are serious due to hospitalization, the reason for hospitalization must be reported as the serious adverse event (diagnosis or symptom requiring hospitalization). A procedure is not

an AE or SAE, but the reason for the procedure may be an AE or SAE. Pre-planned (prior to signing the informed consent form) procedures, treatments requiring hospitalization for pre-existing conditions that do not worsen in severity, and admission for palliative or social care should not be reported as SAEs (see Section 10.2 for definitions).

For deaths, the underlying or immediate cause of death should always be reported as an SAE.

Any SAE that may occur after the on-treatment period that the Investigator assesses as related to study drug should also be reported.

All AEs, SAEs, AESIs, and pregnancy reports are to be reported according to the procedures in Section 10.1.3.

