### 4.2. Secondary Endpoints

The secondary endpoints are:

- Proportion of participants with grade  $\geq 3$  treatment-emergent adverse events (TEAEs), during the EAP and follow-up period
- Proportion of participants with TEAEs leading to study drug discontinuation, during the EAP and follow-up period
- Proportion of participants with treatment-emergent serious adverse events (SAEs) during the EAP and follow-up period
- Incidence of adverse events of special interest (AESIs) during the EAP
- Concentration of each mAb (as applicable to the treatment arm) over time
- Incidence and titer of anti-drug antibodies (ADA), and incidence of neutralizing antibodies (NAb) to each mAb (as applicable to the treatment arm) over time

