#### 11.4.5. Safety Analysis

##### 11.4.5.1. Adverse Events

###### Definitions

For safety variables, the following observation periods are defined:

- The pretreatment period is defined as the time from the signing of the ICF to before study drug administration.
- The EAP is defined as the day from first dose of study drug to day  $169 \pm 7$  days
- The Follow-up period is defined as the end of the EAP to the end of the Follow-up Period (ie, the last study visit).

Treatment-emergent adverse events (TEAEs) are defined as those that are not present at baseline or represent the exacerbation of a pre-existing condition.

This study will collect data on the following targeted TEAEs (Section 10.1): Grade  $\geq 3$  AEs, AEs leading to discontinuation, SAEs, grade  $\geq 2$  hypersensitivity reactions, and grade  $\geq 3$  injection-site reactions.

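### Protocol Section 10.1.1 ends adverse-event recording at an undefined on-treatment period and implies related-only SAE reporting after it, contradicting the all-cause follow-up endpoints and both Schedules of Events

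*Protocol*

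**What the plan says.** Two sentences in protocol Section 10.1.1 set the recording window. Events are to be recorded "from the start of the pretreatment period to the end of on-treatment period (see Section 11.4.5.1". For later events, "Any SAE that may occur after the on-treatment period that the Investigator assesses as related to study drug should also be reported".

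The section cited for the window, 11.4.5.1, lists three periods:

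- Pretreatment: "The pretreatment period is defined as the time from the signing of the ICF to before study drug administration".
- EAP: "The EAP is defined as the day from first dose of study drug to day" 169 ± 7 days.
- Follow-up: "The Follow-up period is defined as the end of the EAP to the end of the Follow-up Period (ie, the last study visit".

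No on-treatment period is among them. The SAP (Sections 4.6.1 and 5.8) gives the same three and adds no fourth.

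The secondary endpoints in protocol Section 4.2 carry no causality limit. One is "Proportion of participants with treatment-emergent serious adverse events (SAEs) during the EAP and follow-up period". The grade ≥3 endpoint likewise counts "treatment-emergent adverse events (TEAEs), during the EAP and follow-up period". The protocol (Section 11.4.5.1, Analysis) plans AE summaries for the EAP and for the EAP and Follow-up combined. The SAP (Section 5.8) plans them for the EAP, for follow-up and for the whole study.

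**The concern.** Section 10.1.1 is where a site looks to decide whether an event is entered. Its cutoff rests on a term that the cited section does not contain, so each site must supply its own meaning. A site that takes the words in their ordinary sense, as the dosing phase or the EAP, would in follow-up omit unrelated SAEs and, under the original schedule, grade ≥3 events. The endpoints and summaries count those same events.

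The gap would fall in a part of the study that matters for safety. Section 3.3.2 relies on follow-up during drug elimination to look for antibody-dependent enhancement. Such a signal could look like ordinary infection and be judged unrelated to drug. Participants with a positive RT-PCR stop assigned drug and move into follow-up (Sections 6.4.5 and 6.4.7), so some follow-up begins just when hospitalisation is most likely to be at issue. After Amendment 2, safety is the only output the plan commits to summarising in full. Efficacy, virology, PK and immunogenicity are optional.

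**Working it through.** There is no stated figure to reproduce. The check is a comparison of passages, followed by day counts that show how much follow-up the ambiguity covers.

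**Step 1: does the cross-reference resolve?** Section 10.1.1 cites 11.4.5.1 for the on-treatment period. Section 11.4.5.1 defines pretreatment, EAP and Follow-up. The SAP does the same. The reference does not resolve.

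**Step 2: does the later-SAE sentence conflict with the endpoints?** Asking specifically for related SAEs after a cutoff has a purpose only if unrelated SAEs are not otherwise required after it. Section 4.2 counts SAEs and grade ≥3 TEAEs through follow-up whatever their cause. If the cutoff falls before the last visit, the two conflict.

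**Step 3: do the schedules settle it?** Table 1 marks grade ≥3 AEs and SAEs through day 253 and at early termination. Table 2 marks SAEs at the end-of-study call with no causality limit. But the AE footnotes (note 7 to Table 1, note 5 to Table 2) send the site to Section 10.1, which holds the cutoff. Neither text is said to prevail over the other.

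**Step 4: how many days are exposed?** Inputs:

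- EAP visit day 169 (±7) and end of study day 253 (Table 1).
- Last Q4W dose day 141 (Table 1). Second and last active Q12W dose day 1 + 84 = day 85.
- Exposure runs to 28 days (Q4W) or 84 days (Q12W) after the last dose (Treatment Exposure, under Section 11.4.5.2).
- End-of-study call 85 days after the last dose (Amendment 2, Table 2).

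Original schedule, for a participant who completes dosing:

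- On-treatment covers all of follow-up: 0 days.
- On-treatment means the EAP: 253 − 169 = 84 days, and 84/253 = 33%. Counted from the end of the visit window, 253 − 176 = 77 days.
- On-treatment follows the exposure definition: 141 + 28 = 169 and 85 + 84 = 169, so again 84 days.

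Amendment 2:

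- 28-day Q4W definition: 85 − 28 = 57 days, and 57/85 = 67%.
- 84-day Q12W definition: 85 − 84 = 1 day.
- On-treatment covers all of follow-up: 0 days.

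A reading tied to study day rather than to the last dose gives no single Amendment 2 figure, because the study day of the last dose varies under early closure.

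**Step 5: what would one missed event do?** The SAP (Section 2.1) gives about 16 to 17 participants per group. One participant's missed SAE lowers that arm's proportion by 1/17 = 5.9 to 1/16 = 6.3 percentage points.

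**The case against.** The strongest reply is that follow-up collection is required in several other places:

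- Section 6.3 uses follow-up visits to gather safety information.
- Both schedules mark SAEs to the last contact, and Table 1 does the same for grade ≥3 AEs.
- The list of targeted events opening Section 10.1 has no time or causality limit.
- Section 10.1.1 itself has investigators look for AEs at every visit.
- Section 10.1.3 asks for all SAEs within 24 hours.
- On deaths, Section 10.1.1 is explicit: "For deaths, the underlying or immediate cause of death should always be reported as an SAE".
- COVID-19 hospitalisations are also captured as medically attended visits, and vital status is recorded in follow-up.

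The sentence on related SAEs is worded as an addition. If on-treatment means everything after pretreatment, it becomes an ordinary post-study rule and nothing is lost. Amendment 2 also says its procedures replace the earlier ones, and a site is unlikely to make the end-of-study call and then discard SAEs that Table 2 lists.

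Much of this stands. A reader might infer that the follow-up endpoints cannot be met, or that the protocol collects only drug-related SAEs after dosing. The documents support neither. The 67% figure is one reading among several. It borrows an exposure definition from a different subsection, and a blinded site could not tell whether 28 or 84 days applied.

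What the reply does not remove is the contradiction. The table footnotes lead back to the section with the cutoff, and the harmless reading is nowhere stated. The death rule and the medically-attended-visit record do not capture non-fatal, non-COVID, unrelated SAEs.

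**Conclusion.** The point holds as an internal contradiction: an undefined cutoff in Section 10.1.1, and a related-only implication at odds with Sections 4.2, 6.3, 9.1 and 11.4.5.1 and SAP Section 5.8. It is wrong as written rather than a debatable design choice, and it should be corrected.

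The supported consequence is a risk that unrelated SAEs in follow-up, and grade ≥3 events under the original schedule, are under-recorded to a degree that varies by site. The exposed stretch is 0 to 84 days under the original schedule for a participant who completes dosing. Under Amendment 2 it is 0 to 57 of the 85 days to the end-of-study call. These ranges cover definitions found in the documents, not every meaning a site might assume. They count days, not events, and nothing in the documents shows that any event was lost.

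All analyses are descriptive in 66 participants with no interim analysis, so no test, power or error rate is affected. What is at stake is the completeness of the safety data.

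One limit on the grade ≥3 endpoint is separate. Table 2 has no row for non-serious grade ≥3 events related to baseline conditions or their treatments, unless they lead to drug discontinuation. That comes from Table 2, and rewording Section 10.1.1 would not change it.

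**What to change.** Make two changes in protocol Section 10.1.1 and send one instruction to sites:

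1. End the recording window at the last study visit, that is, the end of the Follow-up period as defined in Section 11.4.5.1.
2. Apply the sentence on related SAEs to events after the last study visit.
3. Tell sites that SAEs learned of at the end-of-study call are entered regardless of causality, as Table 2 lists.

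This brings Section 10.1.1 into line with the endpoints, the schedules and the planned summaries. The cost is two phrases in the protocol, or a site clarification letter. No visits are added, and at most a few more events are recorded at contacts already scheduled.

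If collection has already finished, query sites about SAEs in follow-up and state in the study report which recording window was applied.
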